2.4.3.2 Dose

To date, CYT107 has not been tested in patients with sepsis. Septic patients frequently have decreased kidney and liver function, changes in circulating blood volume, and loss of vascular integrity with leakage of proteins into the interstitial space.(2) These alterations might impact the pharmacokinetics and pharmacodynamics of CYT107. Thus, we will administer CYT107 using a protocol that is highly similar to a previously protocol that was effective in improving the ALC in patients with cancer, HIV and HCV infections and was well tolerated with a low incidence of serious adverse effects. (12-14)

The dose of 10 μ g/kg, ideal body weight, administered either once or twice a week, will be evaluated in this study. CYT107 at a dose of 10 and 20 μ g/kg once a week has shown an excellent safety profile and biological activity in previous studies in HIV and oncology patients. (12-14, 32)

2.4.3.3 Dosing frequency:

Specificities of CYT107/CYT107R α pathway regulation and data gathered now in humans favor injections once a week and short therapeutic cycles. According to monkey and human data, a three to seven day interval between each injection of CYT107 should lead to full

recovery of CYT107R α expression (CD127) at the surface of T cells which responded to a previous dose of CYT107. Furthermore, a sustained response of T cells to CYT107 should be fully restored, as measured one week later by Ki-67 expression. A weekly interval was successfully tested in the HIV and post HSCT studies aimed at inducing an immune reconstitution- Short cycles, limited to 4 weeks, should avoid inducing exhaustion of T cells responsiveness to high doses of CYT107, which could occur despite the recovery of CD127 expression.

In the specific case of sepsis, there is a real urgency to allow the patients recovering an adequate number of T lymphocytes. Accordingly we will use a twice a week regimen for the very first week of treatment in both groups. Although the recovery of the CYT107 receptor at day 4 is not 100%, it is sufficient to re-stimulate the pool of T cells available for expansion. In the low frequency group we will use this twice a week regimen for the first week only, while it will be used for the full 4 weeks cycle in the high frequency group.

A staggered approach to CYT107 treatment will be used in which treatment will not be initiated in a newly enrolled patient until 24 hours after the previously enrolled patient has received the second dose of CYT107 without evidence of serious adverse event (SAE) occurrence. In cases of a suspected adverse event, a scheduled dose will be postponed by 3 days to allow the adverse event to resolve. For any severe or serious adverse event during the treatment period (as judged by the Investigator), dosing will be suspended and the DSMB will be consulted for case review and advice as to termination of treatment.

2.5 Risk-Benefit Ratio

Sepsis causes extensive apoptotic death of immune effector cells leading to an impaired immune system. CYT107 prevents sepsis induced cell death and improves survival in many clinically-relevant animal models of sepsis. We postulate that by improving host immunity, CYT107 will improve the ability of septic patients to eradicate their primary infection and decrease the incidence of new secondary infections. Given the low risk of adverse effects in patients treated with CYT107 and the potential for benefit, we believe that the risk benefit ratio lies greatly toward use of CYT107 in patients who have a highly likelihood of dying from sepsis; the expected mortality in septic patients who meet the entry criteria for this CYT107 study is approximately 45% at 60 days.

3.0 Objectives of the Trial

3.1 Primary Objective

To study the **biological activity** and **safety** of two dosing regimens of CYT107 at 10 μ g/kg over a treatment period of 4 consecutive weeks:

Twice a week for the first week, followed by:

- Once a week for the low frequency regimen (plus placebo once a week)
- Twice a week for the high frequency regimen
- Control group: will receive placebo (NaCl 0.9%) twice a week

Activity

The primary objective is to demonstrate that treatment of lymphopenic septic patients with CYT107 will reverse the drop in absolute lymphocyte count (ALC) which is a marker of immunosuppression and which correlates with mortality (see Figure 1 and references 4, 21, 23). The effect of CYT107 on the kinetics of the recovery of ALC will be recorded. CYT107 has been demonstrated to increase ALC in a diverse array of patient populations including patients with HIV, patients who underwent bone marrow transplantation, and patients with cancer. Based on the data collected from previous CYT107 studies in Oncology and HIV infection, the treatment of lymphopenic sepsis patients by CYT107 is expected to produce:

- Primary endpoint: increase of ALC by greater than 50% from baseline by day 42 after CYT107 therapy initiated.
- We will also evaluate the number of patients who restore ALC to >1200 cells/mm³ (the lower limit of normal for ALC at most hospitals) by day 42 with the aim of observing this recovery in more than 50% of the patients

These end points will be measured in the three treatment groups (2 dosing frequencies + 1 placebo) at day 42 in both the French and US studies. All patients will undergo randomization for study drug treatment and undergo all study related tests and procedures.

Safety

To characterize the short term safety in a context of a single cycle of CYT107 (4 weeks) administered according to these two dosing regimens in lymphopenic sepsis patients.

3.2 Secondary Objectives

3.2.1 To characterize CYT107 pharmacokinetics (PK) in this patient population

Another secondary objective of the study is to examine the pharmacokinetics (PK) and pharmacodynamics (PD) of CYT107 in patients with sepsis. Septic patients frequently have changes in circulating blood volume, impaired vasculature integrity with leakage of proteins into the interstitial space, and organ dysfunction. Although the investigators expect that CYT107's main PK parameters in septic patients will not be substantially affected by these alterations, it is important to define CYT107 AUC, C_{max} and half-life in this patient population. This information can be used to guide the proper dosing of CYT107 in a larger trial.

Up to now, CYT107 was administered by sub-cutaneous route to patients, but this route of administration is susceptible to increase the immunogenicity of the drug and patient's edema which is frequent in sepsis patients might alter the bioavailability. In this study the CYT107 product will be preferentially given by intra muscular administration. As exemplified for Interferon by Munafo et al(35), FSH by Steinkampf (36) et al., Alefacept by Sweetser (37) et al. and Onercept by Trincharde-Lugan (38) et al., the IM route is known to deliver pharmacokinetic profiles very similar to the S.C. route. Nevertheless the PK profile of CYT107 administered by I.M. will be determined during the study. Nevertheless, septic patients are susceptible to development of coagulopathy, which increases the risk of complications associated with

intramuscular drug administration. Thus, CYT107 will be administered via the subcutaneous route in coagulopathic (INR>2.5, platelet count less than 35,000/ul) patients.

3.2.2 To characterize CYT107 Pharmacodynamics - To determine if CYT107 can restore depressed functional activity of immune effector cells in patients with sepsis.

We will look at the ability of CYT107 to improve common markers of immune function that have been shown to correlate with outcome in patients with sepsis. Note that these tests are not standardized clinically available tests but rather tests that may be useful in the future to help guide administration of immunotherapeutic agents. These tests will be performed in the 3 investigators laboratories by their laboratory technicians.

- Effects to increase monocyte HLA-DR expression
- Effects to increase whole blood LPS-stimulated TNF- α
- Effects on anti-CD3/anti-CD28 stimulated peripheral blood mononuclear cells to produce IFN- γ .
- Effects to increase patient ALC to >1200 and to increase absolute CD4 and CD8 T cell counts.

3.2.3 To assess the impact on number and type of secondary infections:

CYT107 has been highly effective in improving survival in clinically relevant bacterial and fungal animal models of sepsis.(16,18,34) In addition, CYT107 has been effective in boosting immunity and reducing viral loads in patients with HIV and JC virus induced progressive multifocal leukoencephalopathy.(18,12,32) Most recently, CYT107 led to restoration of gut associated lymphoid tissue in HIV patients with a subsequent reduction in markers of inflammation.(31) Thus, we believe that CYT107 will improve host immunity and thereby lead to a decrease in hospital acquired secondary infections in septic patients.

Consequently, we hope to see a decrease in secondary opportunistic type bacterial and fungal infections in septic patients treated with CYT107 compared to septic patients who are treated with placebo (Control group). We will use the Center for Disease Control criteria for definition of ICU-acquired infections. Because it is often difficult to determine if a secondary hospital acquired infection is present, a panel of 3 experienced ICU physicians, “The Secondary Infection Evaluation Committee”, will be used to evaluate and grade whether a secondary hospital acquired infection is present. These 3 physicians will be blinded to patient treatment with CYT107 versus placebo. These 3 physicians will not be members of the investigative team but rather colleagues of the investigators. They will meet either in person or by teleconference once a month or as deemed necessary by the Investigator to judge secondary infections.

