--------------------------	---

Study Design	
This is a phase II, double-blinded, randomized, placebo-controlled study aimed at comparing, two dosing frequencies in lymphopenic patients with sepsis.
 
The study will be performed in the US. A twin study will be performed in France using the same study design so that a common statistical analysis could be performed at the end of the two studies.
 
Patients will be randomized to three arms; CYT107 High Frequency Arm, CYT107 Low Frequency Arm, and Control (standard of care), with a ratio of 1:1:1
 
BLINDING: Patients and care-providers will be blinded as well as outcome assessors.

Sample Size	
A total of 30 evaluable septic patients from US and French sites will be randomized 1:1:1 to receive study drug treatment over 4 weeks:
 
• High frequency: intramuscular (IM) administration of CYT107 at 10µg/kg x2/week x 4 wks (total of 8 doses of CYT107)• Low frequency: IM administration of CYT107 at 10µg/kg x2/ the first week followed by CYT107 and Placebo weekly for 3 wks(total of 5 doses of CYT107 + 3 doses of Placebo)• Control: Will receive 8 administrations of Placebo (twice a week for 4 wks)

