The drug is well tolerated and the most frequent adverse events observed are local erythema at injection site. (12-14, 31)

Activity

[figure not shown]
Recent trials in HIV-infected patients have demonstrated a sustained dose-dependent increase in naïve and memory CD4⁺ and CD8⁺ T cells after administration of r-hCYT107 either with CYT 99 007 or CYT107.(12,30,31) In a prospective randomized placebo-controlled study, a single subcutaneous (SC) dose of r-hCYT107 was well tolerated with biologic activity demonstrable at 3 µg/kg and a maximum tolerated dose (i.e. without SAE or dose limiting toxicity) of 30 µg/kg. Single-dose of recombinant r-hCYT107 increased the numbers of circulating CD4⁺ and CD8⁺ T cells, predominantly of central memory phenotype. Levy et al.¹ published recently the preliminary results of the CYTHERIS study. These results were based on 13 patients who received a total of 8 subcutaneous injections of 2 different doses of r-hCYT107 (CYT 99 007); 3

or 10 µg/kg, 3 times per week (w) over a 16-day period. R-hCYT107 was well tolerated and induced a sustained increase of naive and central memory CD4+ and CD8+ T cells. (12)

We have now confirmed and extended our initial results with the completion of the INSPIRE study conducted in USA, Canada, France, Italy, utilizing the current glycosylated version of r-hCYT107 (CYT107) in HIV patients whose disease was well controlled by HAART but who remained immune non-responders with CD4+ T cells counts below 400/µL.

[figure not shown]
Results from INSPIRE patients confirmed the ability of CYT107 to produce a high quality immune recovery as shown in figure 2. The increases of CD4+ T cells counts induced by the three dosages of CYT107 administrations (10, 20 and 30 µg/kg/week) were significant when compared to the levels observed in the placebo arm (12).

Figure 2 Dose-dependent effect of CYT107 (CYT107) on CD4+T cells

At 20 µg/kg, CYT107 (CYT107) preferentially expanded Naive (N) and Central memory (CM) CD4+ as shown in figure 3.

[figure not shown]
Figure 3 Expansion of Naive (N) and Central Memory (CM) T cells after CYT107, 20 µg/kg

X axis is the ALC/µL. Y axis represents Days (D) or Weeks (W).

[figure not shown]
This expansion was associated with a significant decrease of the “PD-1⁺” exhausted CD4⁺ and CD8⁺ T cells as shown in figure 4:

Figure 4 Decrease of exhausted (PD1⁺) CD4⁺ and CD8⁺ T cells after CYT107

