4.3 Endpoints

4.3.1 Primary Biological Activity & Safety Study Endpoints

- 1) *Weekly measures of absolute lymphocyte counts (ALC)* will be performed to determine the kinetics of restoration of ALC. Specifically, we will quantitate the increase of ALC at day 42 +/- 3 days, expressed as a percentage of baseline value determined at the time point that CYT107 was first administered (day 1). We will determine the number of patients who reach a 50% increase over the baseline value and we will also determine the percentage of patients reaching an ALC > 1200 at day 42 +/- 3 days in each group.
- 2) *Assessment of the clinical, biological, and immunological effects of CYT107* as well as its safety and tolerability, i.e., incidence and scoring of all adverse events: AEs and SAEs all over the study period, ending day 42 +/- 3 days, will be recorded and evaluated by the DSMB, Steering Committee, and secondary infections committee.

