10.2 Data Safety Monitoring Board (DSMB)

The DSMB will be composed of 4 experts who are not involved in the conduct of this trial as investigators but are experienced in the management of Sepsis disease and immunotherapy:

- [name], MD, Brown University School of Medicine, USA
- [name], MD, Vanderbilt University School of Medicine, USA
- [name], PhD, Vanderbilt University School of Medicine, USA
- [name], MD, University of Florida School of Medicine, USA

If need be, the DSMB is free to ask for the advice of one or several other experienced physicians whose name and advice, however, must be communicated to the steering committee.

The mission and rules of DSMB is described in the DSMB charter which will be signed by DSMB member before study initiation.

On an ongoing basis, the DSMB will review:

- All Critical Events.
- All treatment emergent adverse events (TEAEs)
- All SAE assessed by the investigator, by the DSMB, UVEC or by the 3 panel expert committee which adjudicates whether the abnormal finding is secondary to CYT107 or part of the septic process.
- Individual data on the size of lymphoid organs.

The DSMB will review, confirm or discuss the severity grade suggested by the investigator assess the causality relationship to CYT107 and the experimental protocol.

The DSMB will advise the Sponsor regarding study continuation. On an ongoing basis and at the end of the study the DSMB, will review the safety data.

The experts of the DSMB should follow and complete the Causality Assessment Guidelines.

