10.3 Secondary Infections Evaluation Committee

Because it is often difficult to determine if a secondary hospital acquired infection is present, a panel of 3 experienced ICU physicians will be used to evaluate and grade whether a secondary hospital acquired infection is present. These members include: [name], Professor of Surgery, Washington University School of Medicine; [name], Assistant Professor of Anesthesiology and Critical Care Medicine; Washington University School of Medicine. [name], Assistant Professor of Anesthesiology and Emergency Medicine. Washington University School of Medicine.

These 3 physicians will be blinded to patient treatment with CYT107 versus placebo. They will not be members of the investigative team but rather colleagues of the investigators. They will meet either in person or by teleconference once a month to judge secondary infections.

11. Procedures for Special Events

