12.1 Definitions

The following standard definitions for adverse events will be used:

Adverse event: An adverse event is any undesirable or untoward medical event (clinical or non-clinical e.g. abnormal laboratory/EKG/imaging results) which occurs in a patient or in a patient in a clinical trial, who is receiving a pharmacological product, and which is not necessarily causally related to the treatment.

Serious adverse event: A serious adverse event or reaction is any untoward medical occurrence that at any dose:

- results in death
- is life-threatening (the term “life-threatening” in the definition of “serious” refers to an event in which the patient was at risk of death at the time of the event; it does not refer to an event which hypothetically might have caused death if it were more severe.).
- requires inpatient hospitalization or prolongation of existing hospitalization
- results in persistent or significant disability/incapacity
- is a congenital abnormality
- is medically significant (event that may not result in death, be life-threatening, or require hospitalization may be considered serious when, based upon appropriate medical judgment, they may jeopardize the patient or subject and may require medical or surgical intervention to prevent one of the outcomes listed in this definition)

Unexpected Serious Adverse event: An unexpected adverse event is an event, the nature or severity of which is not consistent with CYT107 Investigator's Brochure (updated at least annually).

Critical event: The following events, occurring after the start of CYT107 and considered to be possibly or probably related to the study drug:

- Any grade ≥ 3 Adverse Event (clinical or biological)
- Rash \geq grade 2
- Any diagnosis of lymphoma confirmed by a pathologist
- Any adenopathy compromising or threatening organ function (e.g. mediastinal adenopathy inducing a respiratory distress; inguinal adenopathy inducing an edema of the lower limb; or any adenopathy threatening skin breakdown).
- Splenomegaly that is accompanied by:
 - 1) Clinical hypersplenism
 - 2) Suspicion of a diagnosis of splenic infarct (left upper quadrant pain and imaging study compatible with the diagnosis)
 - 3) Splenic rupture

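### The infection panel is declared blind with one task, but section 4.3.1 also has it evaluate AEs/SAEs, and nothing limits the arm-suggestive data it may see

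*Protocol*

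**What the plan says.** **Blinding and task.** The synopsis (Study Design) states: "Patients and care-providers will be blinded as well as outcome assessors". Section 3.2.3 sets up the Secondary Infection Evaluation Committee, three ICU physicians who judge whether a hospital-acquired secondary infection is present. It says such judgements are often difficult, refers to CDC criteria, and adds: "These 3 physicians will be blinded to patient treatment with CYT107 versus placebo". Section 10.3 repeats the task and the blinding and says of the members: "They will not be members of the investigative team but rather colleagues of the investigators".

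**A second task.** Section 4.3.1, item 2, is headed "Assessment of the clinical, biological, and immunological effects of CYT107" and also covers safety and tolerability. It says that AEs and SAEs up to day 42 "will be recorded and evaluated by the DSMB, Steering Committee, and secondary infections committee".

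**A possible third task.** Section 10.2, listing what the DSMB reviews, refers to a "3 panel expert committee which adjudicates whether the abnormal finding is secondary to CYT107 or part of the septic process". It does not name that body. The infection panel is the only three-member panel the protocol defines.

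**What counts as an AE.** Section 12.1 allows AEs to be "clinical or non-clinical e.g. abnormal laboratory/EKG/imaging results". Section 12.2.1.1 adapts the grading table so that injection-site reactions are captured precisely. Section 2.3.1.3, on previous CYT107 trials, says "the most frequent adverse events observed are local erythema at injection site".

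No section describes the case package given to the panel or lists anything to be masked in it. The SAP names neither the panel nor the secondary-infection endpoint.

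**The concern.** Blinded adjudication protects an endpoint only if the adjudicators' material does not hint at the arm. Sections 3.2.3 and 10.3 describe a panel with one narrow task. Section 4.3.1 gives it a wider one that brings in safety data, including a reaction known from earlier CYT107 use, while the comparator is saline. The protocol neither reconciles the two descriptions nor separates the safety material from the infection judgement.

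Secondary infection is the only clinical efficacy endpoint with an adjudication panel. Section 14.2 says the study is powered to show a reduction in it, and the synopsis hopes for a fall from 35–40% to 25%. Because the calls are acknowledged to be difficult, an adjudicator's impression of the arm could tip borderline cases, and a judgement made with that impression cannot be blinded again afterwards.

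**Working it through.** The plan states no figure on this point, so there is none to reproduce. The check has two parts.

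**1. Roles set side by side**
- Sections 3.2.3 and 10.3: infection judgement only, blinded.
- Section 4.3.1, item 2: the same committee, by name, evaluates AEs/SAEs. This is explicit.
- Section 10.2: attribution to CYT107 by an unnamed three-member body. Identity with the infection panel is possible but not stated.
- Injection-site reactions are AEs (12.2.1.1), so they fall within the 4.3.1 duty as written.
- ALC is item 1 of section 4.3.1, and the committee is named only in item 2. A rise from lymphopenia towards normal is not in itself an untoward event under 12.1. Access to ALC is therefore not stated. It is not excluded either, since no dossier is defined and ALC is reported in the same haematology panel as the white and neutrophil counts (7.1.1).

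**2. How informative ALC would be if it were visible**

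Inputs:
- Allocation 1:1:1 (6.2), so the prior probability of CYT107 is 2/3 = 66.7%.
- Planned proportion with a >50% ALC rise (9.1): above 80% on CYT107 and below 20% on placebo, taken here as 80% and 20%.

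Formula: P(CYT107 | rise) = (2/3 × s) / (2/3 × s + 1/3 × f), where s is the response rate on CYT107 and f the rate on placebo.

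- Plan rates, s = 0.80, f = 0.20: 0.5333 / (0.5333 + 0.0667) = 88.9%.
- Assumed f = 0.40: 0.5333 / (0.5333 + 0.1333) = 80.0%.
- Assumed f = 0.50: 0.5333 / (0.5333 + 0.1667) = 76.2%.

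In the other direction, at plan rates, P(placebo | no rise) = (1/3 × 0.80) / (1/3 × 0.80 + 2/3 × 0.20) = 0.2667 / 0.4000 = 66.7%, against a prior of 33.3%.

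Guessing the arm from ALC alone would be right in 2/3 × 0.80 + 1/3 × 0.80 = 80% of patients, against 66.7% for always guessing CYT107. With f = 0.40 it is 2/3 × 0.80 + 1/3 × 0.60 = 73.3%, and with f = 0.50 it is 70.0%.

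The higher placebo rates are assumptions, but there is reason to consider them. Section 2.1.2.1 reports a gradual ALC rise in sepsis survivors, and section 9.2.3 counts a rise at any measurement up to day 42.

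The injection-site cue cannot be sized, because the documents give no reaction rates for intramuscular CYT107 or for saline.

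**The case against.** The strongest reply is that 4.3.1 is a loose list. The same sentence names the Steering Committee, whose ongoing remit in section 10.1 is only Grade 3 or higher events and Critical Events, so the sentence need not mean that every body reviews every event. Secondary infections can themselves be AEs, and the panel may be listed for those alone. That reading is possible. The text does not say it, which is why a clarification is needed.

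A reader might infer that the panel sees lymphocyte counts and that these reveal the arm. The documents do not support this. No section gives the panel ALC. Even if ALC were visible, the probability of CYT107 starts at 67%, and a rise leaves real uncertainty. It would also help only if the rise were on record when the case was judged.

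A reader might likewise take the body in 10.2 to be the infection panel. That rests on the number three alone. Judging causality does not in itself break a blind either: blinded investigators do it under section 12.2.1.2.

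The erythema experience also needs its context. Section 3.2.1 says CYT107 had until now been given subcutaneously, whereas this trial mainly uses the intramuscular route (8.4). Placebo patients receive injections of the same volume, so an injection-site finding is not specific to CYT107.

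Finally, the CDC criteria in 3.2.3 give the judgement an anchor. All of this limits what can be claimed. It does not remove the conflict between 3.2.3/10.3 and 4.3.1, or supply a rule on what the panel may see.

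**Conclusion.** The point holds as an unreconciled conflict of roles with no safeguard. A panel described as blind with one task is also listed as evaluating AEs/SAEs, which exposes it at least to injection-site findings. It may or may not also be the attribution body in 10.2.

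The cues could suggest the arm without proving it. If ALC were visible, the probability of CYT107 after a >50% rise would go from 67% to 89% at the plan's 80%/20% rates, and to 76–80% if 40–50% of placebo patients respond. This rests on ALC being in the material, which no section states, and on planning rates that may be optimistic.

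The documents do not support a conclusion that the blind is broken, or that the infection result would be biased by any particular amount. That would need a rate at which adjudicators change their calls when they suspect an arm, and the documents give no basis for one. The change is still worth making: the endpoint is partly subjective, the protocol intends to rely on it, and the correction is small.

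**What to change.** 1. **Section 4.3.1:** remove the secondary infections committee from AE/SAE evaluation, or limit its part there to adjudicating suspected infections.
2. **Section 10.2:** name the three-member body. If it is the infection panel, leave attribution to CYT107 with the investigator, sponsor and DSMB, who already assess causality or review SAEs (10.2, 12.2.1.2, 12.3). If it is another body, define it. The role should not simply be deleted.
3. **Sections 3.2.3 and 10.3:** state that adjudication dossiers omit post-baseline lymphocyte counts and percentages, T-cell subsets, injection-site findings and spleen size. Keep total white and neutrophil counts and the other data needed to apply the CDC criteria.

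These changes should be in place before any case is adjudicated. The cost is wording in four sections and modest dossier preparation by existing study staff, since case data come largely from medical records and must be redacted. One leak remains: a total white count shown with a neutrophil count still allows a rough inference about lymphocytes. That is acceptable, because withholding those counts would take away data the panel needs to judge infection.
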